## 6.2.7. Cardiac Imaging

### 6.2.7.1. 12-lead Electrocardiograms

TriPLICATE or single standard 12-lead electrocardiograms (ECGs) will be recorded. The 12-lead ECGs (12-lead at 25 mm/sec reporting rhythm, ventricular rate, PR-interval, QRS complex, QT interval, and corrected QT [QTc] interval) will be performed after the subject has been in the supine position for at least 5 minutes. Data will be captured in the source documents and the CRF.

Whenever vital signs, ECGs and/or blood draws are scheduled for the same nominal time, the ECG will be obtained first, followed by vital signs and then blood draw(s).

### 6.2.7.2. Left Ventricular Ejection Fraction

LVEF will be measured via multiple gated acquisition scan (MUGA), or echocardiogram (ECHO) for all subjects. Follow-up assessments should use the same procedure used at the screening assessment. Data will be captured in the source documents and the CRF.

## 6.2.8. Ophthalmologic Examination

An ophthalmologic examination will be performed by a qualified ophthalmologist at screening as described below in all subjects. The screening ophthalmologic exam will include:

- Visual acuity

- Slit-lamp examination with fluorescein staining following pupillary dilation (unless fluorescein and pupillary dilatation are contraindicated)
- Ophthalmologic examination focusing on the anterior chamber, iris and anterior vitreous

Subsequent ophthalmologic examinations will be performed as clinically indicated. If there are any clinically significant findings, a full ophthalmologic exam will be conducted by a qualified ophthalmologist.

### 6.3. Efficacy Assessments

Tumor assessments will be performed as follows:

**Table 6: Tumor Assessments**

Visit	Assessments
Screening	
Tumor assessments via imaging studies, including computed tomography (CT) and/or magnetic resonance imaging (MRI), of the chest and abdomen and pelvis (including other sites, as appropriate) [or fludeoxyglucose positron emission tomography (FDG-PET) as necessary] will be performed.
 
A brain scan (CT or MRI) will be performed for subjects with known brain lesions.
 
Bone marrow aspirate and biopsy (with cytogenetic analysis, as appropriate depending on cancer type) should be performed for subjects with known or suspected bone marrow involvement.
 
Note: Efficacy assessments (scans, aspirates, and biopsies) obtained within 8 weeks of the first dose of IP and prior to obtaining informed consent as part of standard of care assessments may be used, assuming these assessments meet the protocol requirements.

Day 15 of Cycle 2, 4, 6 and every 3 cycles thereafter (Cycles 9, 12, 15, etc.)  Allowable window: ( $\pm$ 7 days)	
Tumor assessments via imaging studies, including CT and/or MRI, of the chest and abdomen and pelvis (including other sites, as appropriate) [or FDG-PET as necessary] will be performed.
 
A brain scan (CT or MRI) will be performed for subjects with known brain lesions.
 
Bone marrow aspirate and biopsy (with cytogenetic analysis, as appropriate depending on cancer type) should be performed for subjects with known or suspected bone marrow involvement.

End of treatment (may be omitted if performed within the previous 28 days)	
Tumor assessments via imaging studies, including CT and/or MRI, of the chest and abdomen and pelvis (including other sites, as appropriate) [or FDG-PET as necessary] will be performed.
 
A brain scan (CT or MRI) will be performed for subjects with known brain lesions.
 
Bone marrow aspirate and biopsy (with cytogenetic analysis, as appropriate depending on cancer type) should be performed for subjects with known or suspected bone marrow involvement.

After screening, tumor assessments thereafter should be performed using the same CT/MRI scanning modalities used at screening, as permissible.

#### 6.4. Pharmacokinetic Assessments

The schedule for PK assessments is described below:

**Table 7: PK Sampling Time Points**

Visit	Nominal time point	Allowable window
Cycle 1 Day 1	Predose	<15 min prior to dosing
	0.5 hours postdose	± 5 minutes
	0.75 hours postdose	± 5 minutes
	1 hour postdose	± 5 minutes
	1.5 hours postdose	± 5 minutes
	3 hours postdose	± 10 minutes
	5 hours postdose	± 10 minutes
	8 hours postdose	± 10 minutes
Cycle 1 Day 2	24 hours after dose administered on Cycle 1 Day 1 and predose of dosing on Cycle 1 Day 2	<15 min prior to dosing
Cycle 1 Day 10, 11 or 12	Predose	<15 min prior to dosing
	0.5 hours postdose	± 5 minutes
	0.75 hours postdose	± 5 minutes
	1 hour postdose	± 5 minutes
	1.5 hours postdose	± 5 minutes
	3 hours postdose	± 10 minutes
	5 hours postdose	± 10 minutes
	8 hours postdose	± 10 minutes
Cycle 1 Day 11, 12 or 13	24 hours after dose administered on Cycle 1 Day 10, 11 or 12 and predose of dosing on Cycle 1 Day 11, 12 or 13	± 1 hour

Should dose administration CC-122 be interrupted for > 72 hours before the Cycle 1 Day 10, 11 or 12 sampling, serial PK samples will not be collected until ≥ 2 days of CC-122 continuous treatment has been reestablished.

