As of 13 Jan 2016, in Part A the most common treatment-emergent adverse events (TEAEs) (occurring in  $\geq$  20% of subjects overall) were fatigue, which was experienced by 19 (55.9%) subjects; neutropenia, 11 (32.4%) subjects; constipation, 9 (26.5%) subjects; nausea, peripheral edema and asthenia, which occurred in 8 (23.5%) subjects each; and dyspnea and vomiting, 7 (20.6%) subjects each. The system organ class (SOC) categories for which adverse events (AEs) were most frequently reported ( $\geq$  50% of all subjects overall experienced an AE that is categorized in the respective SOC) were Gastrointestinal Disorders, with 70.6% of subjects experiencing an AE in this SOC; General Disorders and Administration Site Conditions, 67.6%; Infections and Infestations, 55.9%; and Blood and Lymphatic System Disorders, with 50.0%.

Other than decreases in white cell counts, no laboratory abnormalities showed clear treatment-related changes. ECG and left ventricular functioning monitoring were unremarkable. Seven subjects had sporadic, asymptomatic, mild troponin-T laboratory test elevations from baseline, with no associated cardiac findings, and no clear association with dose or treatment duration. The subjects continued on study treatment. Subject monitoring and troponin elevation analysis is ongoing.

Preliminary pharmacokinetic analysis of CC-122 administered to subjects with solid tumors and hematologic malignancies demonstrated that CC-122 was rapidly absorbed and eliminated with a mean terminal half-life ranging between 8.3 and 25.2 hours. Overall  $C_{max}$  and AUC increased in a linear, approximate dose proportional manner with dose after single and multiple doses. There was moderate drug accumulation (about 30% to 40%) following repeated daily dosing. In vitro studies indicate mean CC-122 plasma protein binding is approximately 38%.

The preliminary results for best overall tumor response in study CC-122-ST-001 included one complete response (CR), in a subject with follicular lymphoma in the 3 mg QD cohort, and two partial responses (PR), both in subjects with lymphoma (DLBCL and MCL) in the 3 and 3.5 mg cohorts.

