### **3. STUDY ENDPOINTS**

#### **3.1. Primary Endpoint(s)**

The primary endpoints of this study are:

- The following safety endpoints: DLTs, MTD, evaluated using the National Cancer Institute Common Terminology Criteria for Adverse Events (NCI CTCAE) criteria version 4.03
- PK parameters:  $C_{max}$ , AUC,  $T_{max}$ ,  $t_{1/2}$ , CL/F, Vz/F and Accumulation Index of CC-122

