- b After completion of Cycle 1, written informed consent will be obtained again from subjects prior to the start of the second cycle of treatment.
- c As per the PPRMP, screening pregnancy tests must be performed within 10 to 14 days prior to starting dosing. FCBP with regular or no menstrual cycles will undergo postdose pregnancy tests as noted on this table, every week for the first 28 days and every 28 days thereafter until the end of treatment, and 28 days after the last dose of CC-122. However, FCBP with irregular menstrual cycles will undergo weekly assessments for the first 28 days, every 14 days thereafter until the end of treatment and the end of treatment pregnancy test must be performed 14 and 28 days after discontinuing treatment.
- d If screening assessments are performed within 2 days of Cycle 1 Day 1 these assessments do not need to be repeated on Cycle 1 Day 1.
- e Triplicate ECGs (3 recordings within  $2\pm 1$  minute intervals) will be performed only at screening. Single ECGs will be collected for all other visits.
- f During the study, LVEF assessments should be repeated on Day 1 after every three cycles starting with Cycle 3 and when clinically indicated (for example, for decreased cardiac output) using the same modality at screening.
- g Ophthalmology examinations will be performed for all subjects at screening and during the study if clinically indicated.
- h Tumor assessments include imaging studies (via CT/MRI) and may include brain scans, and/or bone marrow aspirate/biopsy depending on tumor type and involvement. After screening, tumor assessments will be performed on Day 15 of Cycle 2, 4, 6 and every 3 cycles thereafter (Cycles 9, 12, 15, etc.), with an allowable window of  $\pm 7$  days. Tumor assessments at the end of treatment visit may be omitted if performed within the previous 28 days.
- i Refer to Section 6.4 for details on PK sampling time points.
- j Starting from Cycle 1 Day 1, CC-122 is administered once a day for 5 continuous days out of 7 days per week.
- k If performed on Day 13, a dose of CC-122 will not be administered.

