##### Intra-subject dose escalation:

The following additional PK samples will only be collected for subjects who were dose escalated from their initial assigned dose (see Sections 8.2.1 and 8.2.9.2):

- After at least 2 days of continuous dosing of CC-122, PK samples should be collected at the following time points:
  - At predose (<15 min prior to dosing), and at 0.5, 0.75, 1, 1.5, 3, 5, 8, and 24 hours postdose

Sample collection kits and detailed instructions for PK sample collection, processing, storage, shipping and handling will be provided to the sites by the central laboratory upon study initiation.

[REDACTED]

[REDACTED]

[REDACTED]

[REDACTED]

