### **8.2.4. Definition of Evaluable Subjects**

A subject evaluable for DLT evaluation is defined as one whom, in the DLT evaluation period, either:

- a. Received at least 85% of the planned doses of CC-122 at the cohort-specified dose in Cycle 1 (at least 17 out of 20 doses for the 5 continuous days out of 7 days per week intermittent dosing cohorts), has sufficient data for safety evaluation by the SRC and has not experienced a treatment-related DLT, or
- b. Received at least one dose of CC-122 and experienced a DLT

Non-evaluable subjects will be replaced in the dosing cohort. An additional subject may be enrolled in each dosing cohort to allow for early drop-outs and to avoid study delays after consultation with the sponsor.

Subjects for whom >20% of PK samples were not collected will also be replaced in order to collect sufficient data for PK analysis.

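### The over-72-hour trigger in section 6.4 lets the second PK profile go ahead after one missed dose, and at the boundary after two, which biases the Accumulation Index downward

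*Combined protocol and SAP*

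**What the plan says.** **Schedule.** Table 3 (note j) sets the dosing pattern: "Starting from Cycle 1 Day 1, CC-122 is administered once a day for 5 continuous days out of 7 days per week". Note k adds, for the 24-hour sample, "If performed on Day 13, a dose of CC-122 will not be administered". Week 1 doses therefore fall on Days 1-5 and week 2 doses on Days 8-12. The second serial profile is taken on Day 10, 11 or 12.

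**The deferral rule.** Under Table 7 the condition is "Should dose administration CC-122 be interrupted for > 72 hours before the Cycle 1 Day 10, 11 or 12 sampling", and the consequence is that "serial PK samples will not be collected until ≥ 2 days of CC-122 continuous treatment has been reestablished". The intra-subject escalation paragraph of 6.4 sets a similar condition without any gap trigger: "After at least 2 days of continuous dosing of CC-122, PK samples should be collected at the following time points".

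**Use of the profile.** Section 3.1 ends its list of primary PK parameters with "and Accumulation Index of CC-122". Section 10.9 does not list the index, and no formula is given.

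**Other rules that might catch the case.** Section 8.2.4 keeps a subject DLT-evaluable with "at least 17 out of 20 doses for the 5 continuous days out of 7 days per week intermittent dosing cohorts" and replaces subjects when more than 20% of PK samples were not collected. Section 8.2.9.3 makes a subject non-evaluable at three missed doses. Sections 10.2 and 10.9 define no PK population and no exclusion for missed doses.

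**The concern.** The protocol treats two days of continuous dosing as the state in which a multiple-dose profile should be taken. It says so after a long interruption and again after intra-subject escalation. Day 10, the earliest sampling day, is also the first week 2 day preceded by two consecutive doses. The trigger does not enforce that state for shorter gaps. A subject who skips the dose on the day before sampling can be profiled as though dosing had been continuous. A subject who skips two doses before Day 11 or Day 12 may be profiled on what is close to a second single dose.

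At stake is a primary PK endpoint and, with it, the multiple-dose Cmax and AUC that go to the Safety Review Committee as available PK data (8.2.1) and may inform the RP2D (4.1.1). The error has one direction: a missed dose can only make multiple-dose exposure look lower.

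**Working it through.** **Inputs.** The first three come from the protocol.
- Doses on Days 1-5 and 8-12, once daily (Table 3, notes j and k).
- Accumulation in the earlier study, section 1.1.3: "There was moderate drug accumulation (about 30% to 40%) following repeated daily dosing".
- Mean terminal half-life 8.3 to 25.2 h (section 1.1.3).
- Assumed: linear kinetics, and an index equal to AUC over 24 h at the profiled dose divided by AUC over 24 h on Day 1.

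**Step 1. Consistency with the plan's figure.** For daily dosing at steady state, R = 1/(1 - r), where r = 2^(-24/t½). Hence r = 1 - 1/R and t½ = 24 × ln 2 / (-ln r).
- R = 1.3: r = 0.2308, t½ = 11.3 h.
- R = 1.4: r = 0.2857, t½ = 13.3 h.

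Both lie inside 8.3-25.2 h, a range that spans R = 1.16 to 2.07. The documents' figures are therefore mutually consistent. This is not a unique reproduction, because half-life is given only as a range.

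**Step 2. Does the trigger fire?** Gap from the last dose taken to the profiled dose:

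| Profile day | One dose missed (day before) | Two doses missed (two days before) |
|---|---|---|
| 10 | 48 h, no | 120 h (last dose Day 5), yes |
| 11 | 48 h, no | 72 h, no (exact boundary) |
| 12 | 48 h, no | 72 h, no (exact boundary) |

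The two-dose case on Day 10 escapes only if the interruption counts unplanned time alone (48 h). The text does not say which count applies.

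**Step 3. Index by superposition.** Index = sum over doses taken of r^(profile day - dose day). For Day 11:
- Uninterrupted: 1 + r + r² + r³ + r⁶ + … = 1.297 (r = 0.2308) or 1.391 (r = 0.2857).
- Day 10 missed: drop r, giving 1.066 or 1.106.
- Days 9 and 10 missed: drop r and r², giving 1.012 or 1.024.

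All cases that pass on time since last dose, at 11.3 h to 13.3 h:

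| Profile day | Uninterrupted | One missed | Two missed |
|---|---|---|---|
| 10 | 1.285-1.370 | 1.054-1.084 | (rule fires) |
| 11 | 1.297-1.391 | 1.066-1.106 | 1.012-1.024 |
| 12 | 1.299-1.398 | 1.068-1.112 | 1.015-1.030 |

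On the unplanned-time count, the Day 10 two-dose case would read 1.001-1.003.

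**Step 4. Size in exposure terms, Day 11.** That subject's multiple-dose AUC is low by 1 - 1.066/1.297 = 18% to 1 - 1.106/1.391 = 20% for one missed dose, and by 1 - 1.012/1.297 = 22% to 1 - 1.024/1.391 = 26% for two.

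**Step 5. Sensitivity, Day 11.**
- t½ 8.3 h: 1.155 uninterrupted, 1.021 with one missed, 1.002 with two.
- t½ 25.2 h: 1.960, 1.443 and 1.176.
- A one-compartment oral model with an assumed absorption rate of 2/h changes the 11.3-13.3 h results by at most about 0.015.

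**Step 6. Effect on a cohort of three, one subject affected, Day 11, arithmetic mean.**
- One missed: (2 × 1.297 + 1.066)/3 = 1.220, down 6%; (2 × 1.391 + 1.106)/3 = 1.296, down 7%.
- Two missed: (2 × 1.297 + 1.012)/3 = 1.202, down 7%; (2 × 1.391 + 1.024)/3 = 1.269, down 9%.

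**Step 7. Would other rules remove the profile?** Two missed doses leave 18/20 = 90%, above the 17-dose floor in 8.2.4 and below the three-dose limit in 8.2.9.3. (Those two sections differ on exactly three missed doses, which does not matter here.) The PK replacement rule counts samples not collected; here all were collected.

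**Step 8. What the two-day condition restores.** With doses on both days before the profile and the previous dose five days before it, the index is 1 + r + r² + r⁵ = 1.285 to 1.369, close to the uninterrupted values.

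**The case against.** **Likelihood.** Subjects are hospitalized throughout Cycle 1 as a rule (section 5), so casual missed doses should be rare among about 15 subjects. The documents give no frequency. This stands, although 8.2.9.3 expressly provides for treatment interruptions in that period.

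**The threshold may be deliberate.** The planned off-days already create a 72 h gap (Day 5 to Day 8), so the trigger can be read as longer than the scheduled gap. That is a plausible origin, but the sampling days are placed to avoid the effect of that gap, so it does not justify an unplanned gap of the same length just before sampling.

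**Boundary and reach.** A reader might infer that any subject who missed the two preceding doses is still profiled. The text does not support that: on time since last dose, Day 10 triggers the rule, and for Days 11 and 12 a few minutes of clock time settle it. The one-dose case does not depend on the boundary.

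**Decision impact.** A reader might also infer that dose escalation would be misdirected. Sections 8.2.5, 8.2.7 and 8.2.8 rest on DLT counts and the global MTD. No accumulation threshold governs any decision, and PK summaries are descriptive, with minimum and maximum shown. Day 1 parameters are unaffected.

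**Detection.** Predose concentrations and dosing records would reveal the missed doses, 10.9 makes the PK assessment conditional on sufficient data, and parts of 6.4 are redacted. Hence the supportable claim is only that no exclusion appears in the visible text, not that none exists.

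**Conclusion.** The point holds with limits. As written, the trigger allows the second profile after one missed dose on any of the three sampling days, and after two missed doses before Day 11 or Day 12 at the nominal 72 h boundary. The index then reads about 1.05-1.11 or 1.01-1.03 respectively, against about 1.3-1.4 uninterrupted.

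These values rest on linear kinetics, an AUC-ratio index that the protocol does not define, and an effective half-life of 11.3-13.3 h. The headline contrast of 1.0 against 1.3-1.4 should not be read as fixed: at 25.2 h the two-dose case on Day 11 is 1.18 against 1.96. The corresponding loss in Cmax was not calculated.

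Severity is low to moderate. The event is uncommon and drives no formal decision, but the bias is one-directional, affects a primary PK endpoint, and carries weight in a cohort of three. This is a cheap improvement.

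**What to change.** **Section 6.4.** Replace the trigger with a condition on every second profile, for example: *The second serial profile is collected only if CC-122 was taken on each of the 2 calendar days before the profile day; otherwise it is deferred to the first later dosing day on which this holds.* This also removes the question of how an interruption is measured.

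**Section 10.9 and the SAP.** Define the Accumulation Index. Compute it, and the multiple-dose Cmax and AUC summaries, only from qualifying profiles. The amendment 03 justification shows that the 2, 3 and 4 mg AIC cohorts have already been through committee review, so for profiles already collected, flag the non-qualifying ones and exclude them from these summaries.

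**Cost.** A few sentences. Some profiles move to the next dosing week: a subject who misses Day 10 and was due on Day 11 would next qualify on Day 17, after doses on Days 15 and 16. If a deferred profile is never collected, 9 of the 18 samples in Table 7 (50%) are missing and the subject meets the replacement rule in 8.2.4, so an additional subject is possible. No samples are added for subjects who complete the deferred profile.

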##### Intra-subject dose escalation:

The following additional PK samples will only be collected for subjects who were dose escalated from their initial assigned dose (see Sections 8.2.1 and 8.2.9.2):

- After at least 2 days of continuous dosing of CC-122, PK samples should be collected at the following time points:
  - At predose (<15 min prior to dosing), and at 0.5, 0.75, 1, 1.5, 3, 5, 8, and 24 hours postdose

Sample collection kits and detailed instructions for PK sample collection, processing, storage, shipping and handling will be provided to the sites by the central laboratory upon study initiation.

[REDACTED]

[REDACTED]

[REDACTED]

[REDACTED]

## 7. STUDY POPULATION

### 7.1. Number of Subjects and Sites

Approximately 15 subjects will be enrolled and treated in approximately 3 sites in Japan. However, the total number of subjects enrolled will depend on the number of dose cohorts needed to establish the MTD/RP2D.

### 7.2. Inclusion Criteria

Subjects must satisfy the following criteria to be enrolled in the study:

1. Understand and voluntarily sign an informed consent document prior to any study-related assessments/procedures are conducted
2. Men and women, 20 years or older, with histological or cytological confirmation of advanced solid tumors or NHL, including those who have progressed on (or are not able to tolerate) standard anticancer therapy or for whom no other conventional therapy exists  
*(Note: subjects with solid tumors or NHL will be enrolled for the first dose level and only subjects with NHL will be enrolled in subsequent dose levels)*
3. ECOG Performance Status  $\leq$  2 for all tumors
4. Subjects must have the following laboratory values:
  - Absolute Neutrophil Count (ANC)  $\geq$  1.5  $\times$  10^9/L
  - Hemoglobin (Hgb)  $\geq$  9 g/dL, drawn at least 7 days after the last RBC transfusion
  - Platelets (Plt)  $\geq$  100  $\times$  10^9/L, drawn at least 7 days after the last platelet transfusion
  - Potassium within normal limits or correctable with supplements
  - AST and ALT  $\leq$  3 x upper limit of normal (ULN) or  $\leq$  5.0 x ULN if liver tumors are present
  - Serum bilirubin  $\leq$  1.5 x ULN; subjects with serum bilirubin  $>$  1.5 x ULN and  $\leq$  2 x ULN may be enrolled if agreed to by the sponsor
  - Serum creatinine  $\leq$  ULN or 24-hour clearance  $\geq$  50 mL/min
  - Negative serum pregnancy test in females of childbearing potential as per the CC-122 PPRMP (Appendix B, Section 19.2)
5. Able to adhere to the study visit schedule and other protocol requirements
6. Must adhere to the PPRMP
  - a. Females of childbearing potential must undergo pregnancy testing based on the frequency outlined in PPRMP and pregnancy results must be negative

- b. Unless practicing complete abstinence from heterosexual intercourse, sexually active FCBP must agree to use adequate contraceptive methods as specified in the PPRMP
  - Complete abstinence is only acceptable in cases where this is the preferred and usual lifestyle of the subject.
  - Periodic abstinence (calendar ovulation, symptothermal, post-ovulation methods) and withdrawal are **not acceptable**
- c. Males (including those who have had a vasectomy) must practice complete abstinence or use barrier contraception (condoms) when engaging in sexual activity with FCBP as specified in the PPRMP
- d. Males must agree not to donate semen or sperm for the duration specified in the PPRMP
- e. All subjects must:
  - Understand that the IP could have a potential teratogenic risk.
  - Agree to abstain from donating blood while taking IP and following discontinuation of investigational product.
  - Agree not to share IP with another person.
- f. Other than the subject, FCBP and males able to father a child should not handle the IP or touch the capsules, unless gloves are worn
- g. Be counseled about pregnancy precautions and risks of fetal exposure

